#### 7.5.1 PRIMARY EFFICACY ANALYSIS

The number and proportion of subjects with complete clearance of baseline warts will be summarized by treatment group and each active dose group will be compared to vehicle using pairwise Pearson's chi-square tests. The odds ratios and corresponding 95% CI will be presented. The pairwise comparisons of each active treatment group to the Vehicle Gel treatment group will be computed without concern for controlling for multiplicity.

Percentages will be calculated out of the number of subjects in the analysis population. Subjects who have a clearance of baseline warts at or before the Week 12 visit will be counted as cleared for the analysis. Subjects who do not have a documented clearance by the end of study, including subjects with missing data at the Week 12 or other assessments, will be considered not cleared for the analysis.

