### 7.5.2 SECONDARY EFFICACY ANALYSES

The number and proportion of subjects with complete clearance of total warts, and the number and proportion of subjects with complete or partial clearance of baseline warts at or by Week 12 will be assessed in a similar manner to the primary efficacy endpoint. The response over time will be similarly assessed for the proportion of subjects and total number of warts with complete clearance of baseline and total EGW/PAW. The time to complete clearance of baseline warts will be summarized. Each active dose group will be compared to vehicle using pairwise Pearson's chi-square tests and the odds ratios and corresponding 95% CIs will be presented.

For those subjects in whom complete clearance of baseline warts is achieved prior to Week 12, recurrence of baseline warts will be assessed.

Descriptive summaries will be provided for percent change in baseline wart counts and total wart counts. Each active dose group will be compared to vehicle using pairwise t-tests and the corresponding 95% CIs for the differences in treatment means will be presented. Subgroup analysis for gender and wart location (EGW/PAW) will also be performed.

The secondary endpoints will include:

- Proportion of subjects with complete clearance of total EGW/PAW at or before Week 12;
- Proportion of subjects with a complete or partial clearance of baseline EGW/PAW at or before Week 12. A partial clearance is defined as a reduction in the number of baseline warts;
- Proportion of subjects with complete clearance of baseline EGW/PAW at Weeks 2, 4, 8 and 12;

- Proportion of subjects with complete clearance of total EGW/PAW at Weeks 2, 4, 8 and 12;
- Proportion of subjects with a complete or partial clearance of baseline EGW/PAW at Weeks 2, 4, 8 and 12;
- Percent reduction in baseline EGW/PAW wart counts at Weeks 2, 4, 8 and 12;
- Count of baseline warts and count of total warts at Weeks 2, 4, 8 and 12;
- Time to complete clearance of baseline warts;
- Recurrence of baseline warts cleared prior to Week 12.

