### 4.4.2. Visit Windows

By-visit analyses will be performed using the reported CRF visit. The one exception is the Week 12/ET visit. For safety endpoints that are not measured at every visit (e.g. lab values and vital signs), the Week 12/ET will be mapped to Week 12 but presented in tables/listings as Week 12/ET. For all other endpoints, for subjects who complete the study, the Week 12/ET visit will be mapped to "Week 12" and used in by visit analyses. For subjects who are early terminations, the Week 12/ET visit will be mapped to "ET" (early term and will not be included in the by visit analyses. The ET visit may be used for LOCF of missing data. The ET visit will be carried forward only to visits for which the ET visit occurred prior to on the last study day of the analysis visit window using the following windows:

Analysis Visit	Visit Window (Based on Study Day)
Week 2	Day 2 to Day 22
Week 4	Day 23 to Day 45
Week 8	Day 46 to Day 71
Week 12	Day 72 +

Table 1: Analysis	Visit	Windows
-------------------	-------	---------

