# 8.2.1. Proportion of Subjects with Complete Clearance of Total EGW/PAW at or Before Week 12.

The number and proportion of subjects with complete clearance of total EGW/PAW will be summarized by treatment group and each active dose group will be compared to its corresponding vehicle group using pairwise Pearson's chi-square tests. The Mantel-Haenszel odds ratios and corresponding 95% CI will be presented.

Subjects who have clearance of baseline warts at or before the Week 12 visit will be counted as cleared for the analysis. Subjects who do not have a documented clearance by the end of study, including subjects with missing data at the Week 12 or other assessments, will be considered not cleared for the analysis.

Subgroup analysis for gender and wart location (EGW/PAW) will also be performed for the ITT populations. The subgroup summaries will be descriptive only with no statistical hypothesis testing performed.

# 8.2.2. Proportion of Subjects with Complete or Partial Clearance of Baseline EGW/PAW at or Before Week 12

The number and proportion of subjects with complete or partial clearance, defined as a reduction in the number of baseline EGW/PAW, will be summarized by treatment group and each active dose group will be compared to its corresponding vehicle group using pairwise Pearson's chi-square tests. The Mantel-Haenszel odds ratios and corresponding 95% CI will be presented.

Subjects who have clearance, complete or partial, of baseline warts at or before the Week 12 visit will be counted as cleared or partially cleared for the analysis. Subjects who do not have a documented clearance or partial clearance by the end of study, including subjects with missing data at the Week 12 or other assessments, will be considered not cleared or partially cleared for the analysis.

## 8.2.3. Proportion of Subjects with Complete Clearance of baseline EGW/PAW at Weeks 2, 4, 8, and 12

The number and proportion of subjects with complete clearance of baseline EGW/PAW at each post-baseline visit will be summarized by treatment group and each active dose group will be compared to its corresponding vehicle group using pairwise Pearson's chi-square tests. The Mantel-Haenszel odds ratios and corresponding 95% CI will be presented.

Imputation of missing data will be performed using a last-observation carried forward (LOCF) method where a missing assessment is replaced by the previous visit's assessment.

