# 8.2.5. Proportion of Subjects with Complete or Partial Clearance of Baseline EGW/PAW at Weeks 2, 4, 8, and 12.

The number and proportion of subjects with complete or partial clearance, defined as a reduction in the number of warts, of baseline EGW/PAW at each post-baseline visit will be summarized by treatment group and each active dose group will be compared to its corresponding vehicle group using pairwise Pearson's chi-square tests. The Mantel-Haenszel odds ratios and corresponding 95% CI will be presented.

Imputation of missing data will be performed using a last-observation carried forward (LOCF) method where a missing assessment is replaced by the previous visit's assessment.

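### LOCF in the SAP's by-visit clearance analyses counts an early leaver's last response, even the loss of one wart, as a Week 12 response that was never documented

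*SAP*

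**What the plan says.** SAP 8.2.3 (complete clearance of baseline warts by visit), 8.2.4 (complete clearance of total warts by visit) and 8.2.5 (complete or partial clearance of baseline warts by visit) carry the same sentence: "Imputation of missing data will be performed using a last-observation carried forward (LOCF) method", with the missing value taken from the visit before. All three are tested arm by arm with Pearson chi-square. The outcome in 8.2.5 is "The number and proportion of subjects with complete or partial clearance, defined as a reduction in the number of warts". SAP section 4 sets no minimum size for that reduction, so one wart is enough.

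SAP 4.4.2 keeps an early leaver's ET visit out of the by-visit analyses, but adds: "The ET visit may be used for LOCF of missing data". It may be carried to any visit whose analysis window has not closed by the ET day. The Week 2 window runs to Day 22, so an ET count at about Day 14 can fill Weeks 2, 4, 8 and 12.

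The primary rule (Protocol 7.5.1, repeated in SAP 8.1.1) has two parts. First: "Subjects who have a clearance of baseline warts at or before the Week 12 visit will be counted as cleared for the analysis". Second, subjects without a documented clearance, "including subjects with missing data at the Week 12 or other assessments, will be considered not cleared for the analysis".

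For visits over time, Protocol 7.5.2 says: "The response over time will be similarly assessed for the proportion of subjects and total number of warts with complete clearance". It gives no by-visit missing-data rule. In the protocol, LOCF appears only in the abbreviation list.

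**The concern.** The primary endpoint credits clearance at any time up to Week 12, including clearance that does not last. The by-visit Week 12 proportions are the tables that could show whether a response is present at the end of treatment. Under LOCF they show this only for subjects who were seen. For everyone else they repeat an older status.

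Two kinds of subject are affected. One stops early, for intolerance or any other reason, with one wart fewer than at baseline, and is tested as a Week 12 responder in 8.2.5. The other reaches zero warts and is then not seen again. Any recurrence in that subject goes unseen, although Protocol 4.2.1 keeps fully cleared subjects in follow-up precisely to look for it. SAP 8.2.9 censors such a subject at the last assessment, so later status is treated as unknown there, while 8.2.3 treats the subject as still clear.

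Early stopping is a real prospect. Protocol 1.5 reports two Cohort 1 subjects with severe local reactions leading to treatment discontinuation within two weeks, and Protocol 6.7 makes severe scores in two or more tolerability categories a reason for discontinuation. The SAP gives no reason for choosing LOCF for these endpoints and plans no analysis with missing as non-response.

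**Working it through.** The plan states no response rate, dropout rate or power, so there is no figure to reproduce. The check has four parts.

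**1. Which subjects does the rule change?** At each of Weeks 2, 4, 8 and 12, score complete clearance as cleared, not cleared or missing. That gives 3 × 3 × 3 × 3 = 81 patterns, of which 27 have Week 12 missing. The last observed status is cleared in 9 + 3 + 1 = 13 of these (last seen at Week 8, 4 or 2) and not cleared in the other 14. LOCF differs from missing = not cleared in exactly those 13. The primary rule also counts all 13 as cleared, and no pattern is a LOCF responder but a primary non-responder. These are counts of patterns, not probabilities.

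Example with assumed counts: 5 of 22 subjects clear by Week 8 and 2 of them then leave. Primary: 5/22 = 22.7%. Week 12 by LOCF: 5/22 = 22.7%. Clearance documented at Week 12, if the other three stay clear: 3/22 = 13.6%.

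**2. Size within one arm.** Let d be the share missing Week 12 and q the share of those whose last status was a response. LOCF raises the Week 12 rate by d × q. Both are assumptions. Results in percentage points:

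| d | q = 0 | q = 5% | q = 10% | q = 25% | q = 50% |
|---|---|---|---|---|---|
| 10% | 0 | 0.5 | 1.0 | 2.5 | 5.0 |
| 20% | 0 | 1.0 | 2.0 | 5.0 | 10.0 |
| 30% | 0 | 1.5 | 3.0 | 7.5 | 15.0 |

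Low q is plausible for complete clearance, and higher q for any reduction in count. About 120 subjects at 3:1 in four cohorts, taken as equal (an assumption), give 120/4 × 3/4 = 22.5 per active arm. One carried response is then 1/22.5 = 4.4 points. The table's extremes are 0 to 0.7 subjects (0.30 × 0.10 × 22.5) for q up to 10%, and 0.6 (0.10 × 0.25 × 22.5) to 3.4 subjects (0.30 × 0.50 × 22.5) for q of 25-50%.

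**3. Size between arms.** The shift in the difference is d(active) × q(active) − d(vehicle) × q(vehicle). With q = 50% in both arms:
- 20% missing in each arm: 10 − 10 = 0 points.
- 30% active, 10% vehicle: 15 − 5 = +10 points.
- 10% active, 30% vehicle: 5 − 15 = −10 points.

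**4. Effect on a test.** These counts are assumed: 23 active and 22 once-daily vehicle subjects (3 cohorts × 7.5 = 22.5), with 5 and 2 missing Week 12. The p-values are from uncorrected Pearson chi-square.

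| Endpoint and rule | Active | Vehicle | p |
|---|---|---|---|
| Complete, missing = not cleared | 6/23 | 1/22 | 0.046 |
| Complete, LOCF, no leaver cleared | 6/23 | 1/22 | 0.046 |
| Complete, LOCF, one active leaver cleared | 7/23 | 1/22 | 0.023 |
| Complete or partial, missing = no response | 13/23 | 9/22 | 0.295 |
| Complete or partial, LOCF, 3 and 1 leavers reduced | 16/23 | 10/22 | 0.102 |
| Complete or partial, LOCF, all leavers reduced | 18/23 | 11/22 | 0.048 |

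This illustration has more leavers on active than on vehicle, which is a choice made here and not a figure from the documents.

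**The case against.** Four stronger readings are tempting, and the documents do not support them.

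- A reader might infer that LOCF turns early leavers in general into responders. It does not. For complete clearance, a leaver who still has baseline warts is not cleared under either rule.
- A reader might infer that LOCF makes the Week 12 table inconsistent with the primary table. The primary also credits a subject who cleared and then left, so on complete clearance of baseline warts the Week 12 LOCF rate cannot exceed the primary rate in the same population. Likewise, SAP 8.2.2 already counts any documented partial clearance at or before Week 12.
- A reader might infer a direct contradiction with the protocol. Protocol 7.5.2 says only that response over time is handled similarly. The same sentence covers a number of warts, for which missing = not cleared has no direct meaning, and it does not mention partial clearance over time. Protocol 7.1 leaves detailed methods to the SAP. The departure is an inference for 8.2.3 and 8.2.4, and for 8.2.5 the point is one of method.
- A reader might infer that the active or less tolerable arms gain. No dropout rates by arm are given. Protocol 1.5 says reactions may come from the active agent or the vehicle, and that the two subjects' treatments were unknown.

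It is also fair to say that the stakes are limited. These are secondary endpoints in a study not powered for efficacy, p-values are not adjusted for multiplicity, recurrence has its own analysis in 8.2.9, and none of these by-visit responder tables is among the interim outputs in SAP Table 2.

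What survives is that a status last seen weeks earlier is tested as a Week 12 response, and no planned table shows the result without that assumption.

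**Conclusion.** The point holds in this limited form. SAP 8.2.3 to 8.2.5, read with 4.4.2, count as Week 12 responders those early leavers whose last status was a response. It matters most for 8.2.5. In 8.2.3 and 8.2.4 it touches only subjects already at zero warts when last seen, and the result does not change at all if there are none.

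The within-arm sizes rest on assumed shares missing Week 12 and assumed last-visit response shares. The direction of any between-arm bias cannot be settled from the documents. The primary result stands as planned. This is a cheap improvement to secondary tables.

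**What to change.** In SAP 8.2.3, 8.2.4 and 8.2.5, replace the LOCF sentence with a by-visit non-response rule: an ITT subject with no assessment at a visit is counted as not responding at that visit. A missed visit between two visits with the same response may keep that response. Keep LOCF as a sensitivity table.

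Write it as a rule of its own, not as an application of 8.1.1, because 8.1.1 credits clearance at any earlier visit. Say also in 4.4.2 whether an ET count taken inside a visit's own analysis window is an assessment at that visit. It is a real observation in that window and can reasonably count there, but should not be carried to later visits in the main table.

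The cost is SAP wording, one extra table and slightly lower by-visit rates. The responder endpoints would also follow a different missing-data rule from the count endpoints in 8.2.6 and 8.2.7, which keep LOCF. A leaver could then show a reduced count at Week 12 in one table and no response in another, so a footnote should explain the difference.

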# 8.2.4. Proportion of Subjects with Complete Clearance of Total EGW/PAW at Weeks 2, 4, 8, and 12.

The number and proportion of subjects with complete clearance of total EGW/PAW at each visit will be summarized by treatment group and each active dose group will be compared to its corresponding vehicle group using pairwise Pearson's chi-square tests. The Mantel-Haenszel odds ratios and corresponding 95% CI will be presented.

Imputation of missing data will be performed using a last-observation carried forward (LOCF) method where a missing assessment is replaced by the previous visit's assessment.

# 8.2.5. Proportion of Subjects with Complete or Partial Clearance of Baseline EGW/PAW at Weeks 2, 4, 8, and 12.

The number and proportion of subjects with complete or partial clearance, defined as a reduction in the number of warts, of baseline EGW/PAW at each post-baseline visit will be summarized by treatment group and each active dose group will be compared to its corresponding vehicle group using pairwise Pearson's chi-square tests. The Mantel-Haenszel odds ratios and corresponding 95% CI will be presented.

Imputation of missing data will be performed using a last-observation carried forward (LOCF) method where a missing assessment is replaced by the previous visit's assessment.

# 8.2.6. Percent and Raw Reduction in Baseline EGW/PAW Counts at Weeks 2, 4, 8, and 12.

Descriptive summaries will be provided for percent and raw change in baseline wart counts at each visit. Raw change will be calculated as (post-baseline count – baseline count). Percent change will be calculated as (post baseline count – baseline count) divided by baseline count times 100. Each active dose group will be compared to its corresponding vehicle group using pairwise t-tests and the corresponding 95% CIs for the differences in treatment means will also be presented.

Imputation of missing data will be performed using a last-observation carried forward (LOCF) method where a missing assessment is replaced by the previous visit's assessment.

# 8.2.7. Count of Baseline Warts and Count of Total Warts at Baseline and Weeks 2, 4, 8, and 12

Descriptive summaries will be provided for count of baseline warts and count of total warts at each visit. Each active dose group will be compared to its corresponding vehicle group using pairwise t-tests and the corresponding 95% CIs for the differences in treatment

means will also be presented. The mean total number of baseline warts and total number of total warts by visit will also be graphically displayed.

Imputation of missing data will be performed using a last-observation carried forward (LOCF) method where a missing assessment is replaced by the previous visit's assessment.

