# 3.7.2 INCLUSION CRITERIA

Each subject must fulfill all of the following inclusion criteria to participate in the study:

- 1. Have a signed written informed consent form (ICF);
- 2. Be male or female, 18 to 50 years of age, inclusive and in good general health;
- 3. Have a minimum of two but not more than 20 EGW/PAW with a maximum total wart surface area less than the area of the subject's palm (approximately 1% BSA);

- 4. If currently receiving treatment for EGW/PAW at the time of screening, be willing to discontinue treatment for 28 days prior to randomization and during the study;
- 5. Women of childbearing potential (WOCBP) must have a negative urine pregnancy test (UPT) prior to randomization;
- 6. WOCBP must agree to use an effective method of birth control during the course of the study and for 30 days after their final study visit;
- 7. Be willing and able to follow study instructions and likely to complete all study requirements.

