#### 3.2.2. Secondary Efficacy Endpoints

The secondary endpoints will include:

• Proportion of subjects with complete clearance of total EGW/PAW at or before Week 12

- Proportion of subjects with a complete or partial clearance of baseline EGW/PAW at or before Week 12. A partial clearance is defined as a reduction in the number of baseline warts.
- Proportion of subjects with complete clearance of baseline EGW/PAW at Weeks 2, 4, 8, and 12
- Proportion of subjects with complete clearance of total EGW/PAW at Weeks 2, 4, 8, and 12
- Proportion of subjects with a complete or partial clearance of baseline EGW/PAW at Weeks 2, 4, 8, and 12
- Count of baseline warts and count of total warts at Weeks 2, 4, 8, and 12
- Percent and raw reduction in baseline EGW/PAW wart counts at Weeks 2, 4, 8, and 12
- Time to complete clearance of baseline warts
- Recurrence of baseline warts cleared prior to Week 12

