## 4.1. Sample Size

This study is not powered to detect a statistical difference in efficacy between treatment groups. Approximately 120 subjects will be randomized into the study in a 3:1 ratio (active:vehicle) at approximately 15 sites in North America. The number of subjects enrolled in any dosing cohort is dependent on the recommendations of the DSMB and enrollment rates. The main objective of this study is to evaluate the tolerability, safety, and efficacy of topical NVN1000 Gel.

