#### **10. Interim Analysis**

There will be 4 Data Safety Monitoring Board (DSMB) meetings during the conduct of this study to evaluate safety and tolerability prior to dose modification. A subset of the final safety and tolerability tables and listings, will be provided to the DSMB for review. Outputs to be provided to the DSMB are documented in the DSMB charter. No inferential statistics or hypothesis testing is planned for the DSMB analyses. DSMB analyses will be unblinded to actual treatment. The analyses for the DSMB will be performed by a separate, independent statistics team.

In addition, an Interim Analysis including efficacy summaries will be conducted upon completion of Cohorts 1 and 2 to assist in the planning of future trials. No stopping rules for futility or early efficacy assessment will be applied as part of the interim analysis. The analysis will only be conducted on the subjects in cohorts 1 and 2, and a subset of tables from the primary analysis will be presented. Pairwise comparisons will be done between each active treatment in the cohorts and Vehicle Gel and nominal p-values will be presented without adjustment. Additionally, no adjustments will be made to p-values in the final analysis as a result of the interim analysis.

The analysis set for the interim analysis will be subjects randomized into one of the first two cohorts. All subjects randomized on or prior to the last randomization date entered into IVRS for Cohort 2 will be included.

Table	Population
Table 14.1-1 Subject Disposition	All Randomized Subjects

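### SAP 8.2.7 tests wart counts at each visit without using the recorded baseline count, so total-wart counts get no change-from-baseline or baseline-adjusted analysis.

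*SAP*

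**What the plan says.** SAP 8.2.7 covers the count of baseline warts and the "count of total warts at each visit. Each active dose group will be compared to its corresponding vehicle group using pairwise t-tests". It adds 95% CIs for the mean differences and LOCF for missing visits, and names no covariate. Its heading includes Baseline as well as Weeks 2, 4, 8 and 12, while the t-test sentence names no visit.

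The change endpoint in SAP 3.2.2 is limited to baseline warts: "Percent and raw reduction in baseline EGW/PAW wart counts at Weeks 2, 4, 8, and 12". SAP 8.2.6 analyses it that way.

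The only other total-wart comparisons are chi-square tests of complete clearance. In 8.2.1, "The number and proportion of subjects with complete clearance of total EGW/PAW will be summarized by treatment group"; in 8.2.4, "The number and proportion of subjects with complete clearance of total EGW/PAW at each visit will be summarized by treatment group".

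Protocol 7.5.2 says "Descriptive summaries will be provided for percent change in baseline wart counts and total wart counts", followed by pairwise t-tests. That can be read as percent change for both counts, or as percent change for baseline warts plus a plain summary of total warts.

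The starting count is available. Protocol 4.2.1 has baseline and total warts counted at Baseline. Under the SAP section 4 definitions the two are equal at that visit. Inclusion criterion 3 (protocol 3.7.2) reads "Have a minimum of two but not more than 20 EGW/PAW". Neither document contains a baseline-adjusted model, and SAP 4.2 names no stratification factor.

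SAP 10 states that "an Interim Analysis including efficacy summaries will be conducted upon completion of Cohorts 1 and 2 to assist in the planning of future trials". Its Table 2 lists the total-wart count as Table 14.2-9.1.

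**The concern.** Entry permits a ten-fold range of starting counts, and a subject who starts with many warts can be expected to have more left later. A t-test on the visit count leaves that variation in the error term. It also lets any chance imbalance between small groups carry into the estimated difference. Nothing in the randomisation balances starting count.

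For baseline warts, 8.2.6 largely deals with this. For total warts there is no such analysis. The protocol synopsis names the total number of warts at Week 12 among its secondary endpoints. At the interim, the other efficacy tables (clearance, clearance by gender, percent change) all concern baseline warts, so the total count is the only efficacy output there that includes new warts. An imprecise or imbalanced estimate would therefore feed directly into planning later trials.

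**Working it through.** **1. Which analyses use the starting count**

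| | Baseline warts | Total warts |
|---|---|---|
| Complete clearance, chi-square | 8.1.1, 8.2.3 | 8.2.1, 8.2.4 |
| Raw and percent change, t-test | 8.2.6 | none |
| Visit count, t-test | 8.2.7 | 8.2.7 |
| Baseline-adjusted model | none | none |

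The documents state no power, SD or correlation, so there is no planned figure to reproduce.

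**2. Group sizes (assumed).** SAP 4.1 leaves these open: "The number of subjects enrolled in any dosing cohort is dependent on the recommendations of the DSMB and enrollment rates". For illustration, 120 / 4 = 30 per cohort. At 3:1 that is 22.5 active and 7.5 vehicle. SAP 8.1.1 splits vehicle by dosing frequency, so QD vehicle pools to 3 x 7.5 = 22.5 and BID vehicle stays at 7.5. Rounded, a QD comparison is 22 v 22 (N = 44) and the BID comparison is 22 v 8 (N = 30).

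**3. Precision.** Let rho be the within-arm correlation of starting and visit count. Including the cost of estimating the slope, the variance of the ANCOVA difference relative to the t-test difference is

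(1 - rho^2) x (1 + 1/(N - 4)).

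The second factor is 1 + 1/40 = 1.025 at N = 44 and 1 + 1/26 = 1.038 at N = 30. CI narrowing is 1 minus the square root of the ratio.

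| rho | 1 - rho^2 | Ratio, 22 v 22 | CI narrower | Ratio, 22 v 8 | CI narrower |
|---|---|---|---|---|---|
| 0.3 | 0.91 | 0.933 | 3% | 0.945 | 3% |
| 0.5 | 0.75 | 0.769 | 12% | 0.779 | 12% |
| 0.7 | 0.51 | 0.523 | 28% | 0.530 | 27% |

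Break-even is rho = sqrt(1/(N - 3)): sqrt(1/41) = 0.16 and sqrt(1/27) = 0.19. At rho = 0 the CI widens by sqrt(1.025) - 1 = 1% or sqrt(1.038) - 1 = 2%.

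**4. Chance imbalance.** By normal approximation, the starting means differ by more than 0.5 SD with probability 24% for 22.5 v 7.5 and 9% for 22.5 v 22.5. If starting counts were uniform over 2-20, the SD would be about 5.5 and half of it about 2.7 warts. In 20,000 simulated null trials per setting the t-test held its overall level (4.8-5.2%). Given such an imbalance, its null rejection rate at rho 0.3 / 0.5 / 0.7 was about 6-7 / 10 / 15% (BID) and 8 / 14 / 25% (QD).

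**5. Simulated counts with new warts.** All inputs are assumed: starting count 2-20, mean 7.0, SD 4.3; 40% v 70% of baseline warts left, so slopes differ by arm; 0.8-3.0 new warts per subject; 10,000 trials per scenario. Entries are the SE of the total-count difference, t-test to ANCOVA, with the observed within-arm correlation in brackets.

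| Scenario | 22 v 22 | 22 v 8 |
|---|---|---|
| 1 | 0.99 to 0.70 (0.71) | 1.45 to 0.98 (0.65) |
| 2 | 1.15 to 0.92 (0.60) | 1.66 to 1.29 (0.54) |
| 3 | 1.98 to 1.87 (0.38) | 2.74 to 2.56 (0.33) |
| 4 | 2.94 to 2.89 (0.29) | 4.05 to 3.97 (0.26) |

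At 22 v 22 the SE falls by 29%, 20%, 6% and 2%. ANCOVA coverage of the 95% CI was 94.5-96.1%. With 70% left in both arms, type I error was 3.7-5.2% for ANCOVA and 3.9-5.3% for the t-test. Scenario 4 needs very dispersed new-wart counts: an SE of 2.94 at 22 v 22 implies an SD of 2.94 / sqrt(2/22), about 9.8 warts.

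**6. Interim.** Only Cohorts 1 and 2 contribute, so QD vehicle comes from Cohort 2 alone. If vehicle is split by frequency, both interim comparisons are about 22 v 8. SAP 10 does not say whether vehicle is split there; pooled, it would be about 15.

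**The case against.** Nothing here is invalid. The trial is declared not powered for efficacy, p-values are unadjusted for multiplicity, and the interim has no stopping rule, so preferring ANCOVA to a t-test on a secondary count is a question of efficiency. That stands and sets the weight of the point.

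For baseline warts, 8.2.6 already tests change, so the real gap is total warts. That stands too. An imbalance would also be visible, because baseline counts are summarised and means plotted by visit; but seeing it does not correct the interval.

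The gain may be small for the endpoint that matters. Total counts include new warts, and SAP 8 mixes subjects on a first course, off treatment and on re-treatment, which may lower the correlation. A further simulation let some subjects clear all baseline warts (assumed 30-60% active, 10-30% vehicle). The SE fell by 14-22% with few new warts, 6-12% with moderate numbers and 0-1% with highly dispersed ones. The 27-28% figure is therefore an upper-end case.

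The heading's mention of Baseline is a slight matter, since SAP 3.2.2 and Table 2 name only Weeks 2 to 12. Finally, protocol 7.5.2 itself names t-tests, so changing the test means aligning the protocol wording or recording the departure.

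**Conclusion.** The point holds, as an optional improvement. SAP 8.2.7 ignores a recorded baseline value, and total-wart counts have no change-from-baseline or adjusted analysis anywhere in the SAP. The consequence is avoidable imprecision and exposure to chance imbalance. It is not bias, and overall type I error is not inflated. The primary endpoint and the 8.2.6 percent-change test are untouched.

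The expected narrowing of the CI is about 3% to 28% over correlations of 0.3 to 0.7, against a loss of 1-2% if the correlation is zero. The correlation and the group sizes are assumptions. The finding about what the SAP omits needs neither.

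**What to change.** In SAP 8.2.7, replace the t-tests at Weeks 2, 4, 8 and 12 with ANCOVA (visit count on treatment and baseline wart count), using the same pairwise comparisons and the same LOCF data. Report the adjusted mean difference and its 95% CI. Use the same model for the total-wart count in interim Table 14.2-9.1. Keep the descriptive tables and the 8.2.6 percent-change test.

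State that Baseline counts are summarised descriptively only. Reconcile protocol 7.5.2 with the SAP on whether percent change in total warts is planned, and align its t-test wording. If the sponsor prefers to leave the protocol's test in place, the ANCOVA can be reported beside it.

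The cost is SAP wording, a few lines of code, one degree of freedom per comparison and the protocol alignment. No new data are needed.
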